## DATA COLLECTION:

Responses to measures at all assessment time points are collected with each partner individually with the other partner leaving the room to avoid coercion or fear of reprisal if one partner were to disclose disqualifying information such as domestic violence. Participants will complete the following measures prior to study enrollment to determine if inclusion/exclusion criteria are met:

- *PTSD Checklist for DSM-5* (PCL-5; Weathers et al., 2013) – 20-item self-report measure for the past month that assesses symptoms of PTSD based on the DSM-5; scores at or above 33 indicate probable PTSD. Couples will be included if the veteran partner scores at or above 33 on this measure.
- *Columbia-Suicide Severity Rating Scale* (C-SSRS; Posner et al., 2011) – 8-item self-report measure of suicidal ideation, plan, and intent. Individuals who endorse acute suicidality will be excluded from the study.
- *IPV Assessment-Extended* (IPV-5) – assesses behaviors that individuals engage in during conflict with their partner as well as past and current fear and intimidation in the relationship. Couples with individuals who endorse any severe physical assault behaviors in the past year will be excluded from the study.
- *Alcohol Use Disorders Identification Test* (AUDIT; Bohn et al., 1995) – measures problematic substance use. Individuals endorsing symptoms of an active substance use disorder will be excluded.

Additional measures administered at baseline assessment only include:

- *Traumatic Life Events Checklist* (TLEC; Blake et al., 1995) – a 17-item self-report scale that assesses for a lifetime history of exposure to traumatic events (veteran only)
- *Demographic information and past experiences receiving mental health treatment* (both partners)
- *Coronavirus Stressor Survey* – assesses stress related to COVID19 (both partners)

The primary (relationship satisfaction) and secondary (PTSD symptoms, quality of life) outcomes will be assessed with both partners at baseline, post-intervention, and three months post-intervention using the following quantitative measures:

- *Couples Satisfaction Inventory-32* (CSI-32; Funk & Rogge, 2007) – a well-validated measure of relationship satisfaction
- *Changes in Sexual Functioning Questionnaire Male Clinical* (CSFQ-M; Keller et al., 2006) – the male version of a 14-item measure that provides a brief measure of sexual functioning with good construct validity and internal reliability
- *Changes in Sexual Functioning Questionnaire Female Clinical* (CSFQ-M; Keller et al., 2006) – the female version of a 14-item measure that provides a brief measure of sexual functioning with good construct validity and internal reliability

- *Intimate Safety Questionnaire* (ISQ, Cordova & Blair, 2014) – a 28-item measure of the degree to which partners feel safe being vulnerable with each other across several different domains of the relationship
- *PCL-5* – described above for PTSD+ partner. Will also include version for non-PTSD+ participants (PCL-C) that asks about the extent to which they perceive their partners have experienced PTSD symptoms in the past week
- *Brief Inventory of Psychosocial Functioning* (B-IPF; Kleiman, Bovin, & Black, 2020) – a 7-item self-report measure of past month psychosocial functioning with good psychometric properties. The measure will be amended to assess functioning in the past two weeks and administered biweekly with the CSI-4 throughout treatment.
- *World Health Organization Quality of Life – BREF* (WHOQOL-BREF; The WHOQOL Group, 1998) – assess quality of life. It consists of 26 items that measure physical and psychological health, social relationships, and environment.

Measures for other broader outcomes to be assessed at baseline, post-intervention, and three months post-intervention include:

- *Dyadic Adjustment Scale-7 (DAS-7)* (Hunsley, Best, Lefebvre, & Vito, 2001) – the self-report DAS-7 is based on the original 32-item measure. It assesses domains of relationship functioning and has demonstrated strong psychometric properties
- *Patient Health Questionnaire-9 (PHQ-9)* (Kroenke, Spitzer, & Williams, 2001) – measures depressive symptomatology
- *Brunnsviken Brief Quality of Life Scale (BBQ)* (Lindner et al., 2016) – measures subjective quality of life
- *Significant Others Responses to Trauma (SORTS) Inventory* (Fredman et al., 2014) – measures partner responses to PTSD symptoms and will be completed by non-PTSD+ partners only
- *Experiences in Close Relationships-Revised (ECR-R)* (Franley, Waller, & Brennan, 2000) – measures adult attachment style

Measures administered at post-assessment only include:

- *Client Satisfaction Questionnaire* (Attkisson, 1982) – measures client satisfaction with the intervention they received
- *Qualitative Feedback Questionnaire* – captures verbal feedback from participants regarding their experience of the study

Prior to each B-CBCT session, each participant will complete brief self-report assessment measures for the primary and secondary outcomes. The outcomes measures are listed below. The Veteran participant will complete a questionnaire assessing any side effects of the intranasal Oxytocin. If the Veteran participant is able to become pregnant, she will also take a pregnancy test.

- *PCL-5* and *PCL-C* (Weathers et al., 2013) – past-week version for PTSD+ participant and partner respectively
- *Couples Satisfaction Inventory-4 (CSI-4)* (Funk & Rogge, 2007) – a well-validated and brief (i.e., 4 items) measure of relationship satisfaction completed by both partners

No PII will be stored with participants' data; data will be identified by coded study identifier only. Electronic deidentified data will be stored on restricted VA research servers accessible only on VA-networked, password protected computers. Records linking coded study identifiers to participants' identifiable information will be kept separately from any data, and electronic records will be password-protected. Any hard-copy data (e.g., transcribed questionnaires) will be stored in locked file cabinets in locked offices in [name] office space in the San Diego VMRF/HSR&D Building (Building 13), with any identifiable hard-copy data being stored separately from coded research data.

If able to become pregnant (i.e., assigned female at birth, fertile, following menarche and until becoming post-menopausal unless permanently sterile), the Veteran participant will be required to take a pregnancy test (provided by study staff) at baseline assessment and weekly during treatment before self-administration of oxytocin. A participant is considered not able to become pregnant if they are premenarchal, surgically sterile (documented hysterectomy, bilateral salpingectomy, bilateral oophorectomy, and/or tubal ligation), postmenopausal, or assigned male

at birth. These pregnancy tests will be purchased by the study and mailed to Veteran participants who are able to become pregnant only. Veteran participants who are able to become pregnant will be required to verbally confirm a negative result prior to continuing with each oxytocin administration.

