### STUDY DESIGN OVERVIEW:

This pilot study will enroll up to 20 couples (40 individuals) in B-CBCT + OT over this 12-month project. Participants will be recruited from the San Diego VA Healthcare System. Couples will participate in 8 sessions of B-CBCT augmented with 40 IU of intranasal oxytocin administered 30 min before each session. At baseline and post-treatment, dyads will be asked to complete brief assessments of the outcomes described above. After treatment, they will also provide feedback about factors associated with feasibility of methods and treatment engagement. Quantitative and qualitative data will be used to assess the feasibility and acceptability of the intervention and will be utilized in preparing a proposal for an RCT. We will compare within-group effect sizes on PTSD and relationship satisfaction to effects observed within the historical controls from [name] RCT of B-CBCT.

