#### DESCRIPTION OF INTRANASAL OXYTOCIN:

A 40 IU dose of oxytocin will be self-administered by the Veteran with PTSD only (not the partner) intranasally 30 minutes prior to the start of each weekly B-CBCT session. A 40 IU dose has demonstrated extensive safety and efficacy, is within the normal dosing range, and is one of the most common concentrations utilized in human research. The medication administration protocol is based on previous research by [name] (Collaborator), a leading oxytocin researcher in the area of PTSD, and others. While intranasal oxytocin has most frequently been used in studies utilizing single doses, several recent published studies of repeated dosing have provided evidence of safety in clinical populations, including a study of once-weekly dosing for eight weeks among Veterans with PTSD conducted by Drs. [name] and [name] (Collaborators).

The study prescriber ([name]) will verify study eligibility and provide prescriptions for oxytocin to the VA Research Pharmacy. Oxytocin will be compounded, refrigerated, and shipped directly to the participant's home with administration and refrigerated storage instructions by Harbor Compounding Pharmacy in Costa Mesa, CA with operational support from the VA Pharmacy, which will be responsible for sending prescriptions and documenting the medication in Veterans' medical charts. Research staff will instruct participants on the correct method of administration to achieve the 40 IU dose and will observe participants' self-administration via Veterans Video Connect (VVC). Participants will blow their nose, exhale through their nose, then spray into one nostril while inhaling, alternating nostrils until the 40 IU dose is achieved. Side effects and adverse events will be evaluated weekly.

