## Section 10 - Human Subjects

**10) Describe the characteristics of the proposed subject population. Include age, gender, ethnicity, and health status as appropriate. Note: Data about people are still considered "human subjects" by the IRB, so even if you do not intend to contact the patients whose charts you will review, you still describe the characteristics related to the subjects whose charts you will review.**

- Provide inclusion and exclusion criteria as appropriate. Provide a statement how non pregnancy is confirmed if pregnancy is an exclusion criteria.
- For multisite studies, provide the total number of subjects from all sites and include description of the local site's role as a coordinating center if applicable.
- Indicate the number of VA participants to be studied.
- Indicate the estimated number of consented subjects that will fail the screening process, if any.

A total of 40 participants will be enrolled: 20 Veterans plus their partners (who may or may not also be Veterans). Therefore, between 20 and 40 VA participants will be studied.

Inclusion criteria for the study will be a veteran enrolled in the San Diego VA Healthcare System with a Posttraumatic Stress Disorder Checklist-5 score of > 33, indicating a likely PTSD diagnosis. Veterans must agree not to receive other individual or conjoint psychotherapy for

PTSD during participation in the study. If already on psychoactive medication prior to study referral, Veteran participant must also be on a stable psychoactive medication regimen for at least 45 days.

Exclusion criteria will be acute suicidality; psychosis; active substance use disorder; severe ongoing medical problems, including heart disease and neuroendocrinological disorders (e.g., diabetes); uncontrolled hypotension (systolic blood pressure <100 mm Hg) or hypertension (>160/100 mm Hg); pregnancy, delivery in the past 6 months, or current breastfeeding; or severe intimate aggression reported by either partner (established with validated measures). Because the effects of oxytocin on pregnancy outcome are well known, pregnant and lactating females will be excluded from the trial. We will instruct participants who are able to become pregnant to use appropriate forms of contraception, and we will instruct them to perform urine pregnancy tests at baseline and weekly during treatment before self-administration of oxytocin if a Veteran participant is considered able to become pregnant.

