Potential physical risks are related to participant use of Oxytocin. Oxytocin is a neuropeptide hormone commonly administered intravenously to women during labor and delivery. Risks associated with oxytocin administration have been observed with intravenous, but not intranasal administration, related to its Food and Drug Administration (FDA)-approved purpose to induce labor and facilitate lactation. Risks include seizures, mental disturbances, nausea, vomiting, irregular heartbeat, high blood pressure, and unexpected bleeding or contraction of the uterus and have been observed in a small number of women. Previous studies show that risks of intranasal oxytocin administration are minimal and manageable through the proposed human participants protection methods described below (see 4B. Adequacy of Protection from Risk). Collaborator [name] has administered intranasal oxytocin at the planned dose of 40 international units (IU) to over 900 research participants to date, including Veterans with PTSD and distressed couples with alcohol use disorder and intimate partner violence, without a single severe adverse event reported. Oxytocin is contraindicated for pregnant and lactating women, who will be excluded from the trial. Participants may also experience physical or psychological discomfort during the medication self-administration.

Social risks of this study center around potential threats to confidentiality. We do not anticipate risk of physical, legal, or financial harm as a result of participating in the study. Measures to minimize the identified psychological and social risks are described in Protections Against Risks. Overall, we feel that we have stringently addressed potential risks to participants and that the benefits of the treatment outweigh the risks. Rare but serious risks are with the handling of medical and research records, as there is always the possibility of a breach of confidentiality.

Alternative psychosocial treatments generally include individual treatment for PTSD as well as non-trauma-focused couples counseling provided in an office-based setting similar to the standard services condition offered in our study as well as pharmacological treatments for disturbances in mood, arousal, and sleep often associated with PTSD symptomatology. The risks

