If participants do experience notable distress, they will be provided with contact information for licensed psychologists on study staff, including the PI, and follow-up referrals as appropriate. In addition, they will be given access to a 24-hour crisis psychiatry telephone service. However, our prior research suggests that data collection using the aforementioned procedures can be conducted without undue psychological distress or exacerbation of symptoms among participants. This experience includes substantial research with distressed couples and with technology-mediated interventions. In the event of an Adverse Event (AE), Serious Adverse Event (SAE), or Unanticipated Problem Involving Risks to Subjects or Others (UPR), all notification procedures outlined in the Data Safety and Monitoring Plan section will be followed.

Steps to protect against risk associated with intranasal oxytocin administration will be taken. During informed consent, participants will be informed about the potential side effects of intranasal oxytocin. Participants will not be enrolled unless the study psychiatrist, [name], concurs that no oxytocin-related exclusion criteria are met and the Veteran participant is eligible. Participants will self-administer intranasal oxytocin while being monitored on video by research staff who have ready access to clinicians who can consult on the need for emergency care, if necessary. They will be closely monitored by the research team after each drug administration. Women who are pregnant and lactating women will be excluded from the trial. We will instruct participants who are able to become pregnant to use appropriate forms of contraception, and we will instruct them to perform urine pregnancy tests at baseline and weekly during treatment before self-administration of oxytocin if a Veteran participant is considered able to become pregnant.

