## Section 18 - Risk/Benefit Analysis

### 18) Discuss why the risks to subjects are reasonable in relation to the anticipated benefits to subjects and in relation to the importance of the knowledge that may reasonably be expected to result.

Risk from participating in B-CBCT augmented with intranasal oxytocin is relatively minor in comparison with the potential benefits to relationship quality and PTSD symptoms to be gained by Veterans and their partners in this study, and is not anticipated to be any greater than risks they may encounter during standard clinical care. This investigation may help subjects manage the symptoms and functional impairment associated with PTSD and will provide valuable knowledge about the treatment of PTSD in Veterans. Furthermore, it may also help couples manage and improve relationship problems and associated functional impairment and will provide valuable knowledge about the treatment of relationship distress in Veterans with PTSD. Thus, the risk benefit ratio warrants this study being conducted.

This conclusion is supported further by the protection procedures in place to address any discomfort caused by the assessment or treatment to Veterans and partners. There is minimal risk associated with gathering information about emotional symptoms and taking part in a brief treatment for such symptoms based on an evidence-supported, manualized intervention. There are no aspects of this study that place participants at additional physical, psychological, social, legal or other risk outside of routine medical and mental health care. Risks associated with oxytocin consumption are mitigated by excluding pregnant women, conducting weekly pregnancy tests for Veteran participants who are able to become pregnant, and weekly questionnaire completion regarding any side effects of the oxytocin. Finally, we are mitigating the current risk of COVID-19 exposure by allowing participants to remain in their homes by using entirely virtual (telehealth, web, and phone) procedures for study enrollment and consent, intervention, and assessment. This study uses the existing VA telehealth infrastructure, including secure VVC telehealth appointments and Webex.

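### For Veterans who could become pregnant, each oxytocin dose is released on a spoken report of a home test, although staff already watch dosing by video and could see the device (minor)

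*Protocol*

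**What the plan says.** The Protocol treats pregnancy as an exclusion (Section 9, PARTICIPANTS; Section 10). Section 14 adds: "Oxytocin is contraindicated for pregnant and lactating women, who will be excluded from the trial".

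For Veterans who could become pregnant, Section 10 describes the testing as an instruction: "we will instruct them to perform urine pregnancy tests at baseline and weekly during treatment before self-administration of oxytocin". Section 15 says the same. The data collection part of Section 9 gives the operating rule. The study buys the tests and mails them to these Veterans, and "Veteran participants who are able to become pregnant will be required to verbally confirm a negative result prior to continuing with each oxytocin administration".

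Dosing itself is supervised. The design overview has the 40 IU dose "administered 30 min before each session", with eight sessions planned. Section 15 states: "Participants will self-administer intranasal oxytocin while being monitored on video by research staff". The description of intranasal oxytocin in Section 9 also has staff observe by video.

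Section 18 lists "conducting weekly pregnancy tests for Veteran participants who are able to become pregnant" among the steps that mitigate oxytocin risk. Section 9.8 lists the pregnancy test among the study instruments without saying who reads it.

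**The concern.** Staff see the spray being used but need not see the test result that permits its use. A Veteran who misreads a faint or invalid test, or who skips a test and reports it as negative, would go on to take that week's dose, and nothing in the stated procedure would show it beforehand.

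This matters because the pre-dose test is the only step in view that detects a pregnancy beginning during treatment. The phone screen and the psychiatrist's eligibility review come before enrolment. Contraception advice lowers the chance of pregnancy but detects nothing. The form's own prompt in Section 10 asks how non-pregnancy is confirmed; the answer there is an instruction to test, and Section 9 adds only the Veteran's word.

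At stake is possible exposure of a pregnant participant to a drug from which the Protocol excludes pregnant women. No endpoint, sample size or model in the SAP depends on it.

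**Working it through.** The plan gives no figure to reproduce. The check sets the relevant text side by side and then counts.

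**Who reads the test**

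| Place in Protocol | What it requires | Staff see or record the result? |
|---|---|---|
| Section 9, data collection | Mailed test at baseline and weekly; spoken confirmation before each dose | No |
| Section 9.8 | Lists the test as an instrument | Not stated |
| Section 10 | Veteran is instructed to test | Not stated |
| Section 15 | Veteran is instructed to test; dosing watched on video | Dosing yes, test not stated |
| Section 18 | Counts the weekly tests as a mitigation | Not stated |

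The Protocol does not forbid staff from looking at the device; it does not require it.

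**Counts**

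Inputs: 8 sessions with one dose each and 40 IU per dose (Section 9, design overview); one baseline test plus a test before each dose (Section 9, data collection); 20 Veterans (Section 9, participants). I assume one weekly test per dose.

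- Tests per Veteran who could become pregnant: 1 + 8 = 9, of which 8 directly precede a dose.
- Doses released on one wrong report: 1, that is 40 IU.
- Next scheduled check after a wrong report: the following weekly test for doses 1 to 7; none after dose 8.
- Spoken confirmations in the whole trial: number of such Veterans × 8. That number is not stated. At the extremes, 0 × 8 = 0 and 20 × 8 = 160.

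Expected exposures would also need the chance of pregnancy during treatment and the rate of misread or skipped tests. The documents give neither, so no expected number can be computed, and it may be zero.

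**Privacy at the test**

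Section 9 has each partner complete measures at the assessment time points "with the other partner leaving the room to avoid coercion or fear of reprisal". No text in view extends this to the test before each dose.

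**The case against.** The strongest case against is that the plan already has a complete rule: who is tested, who supplies the test, when it is done, and a condition that must be met before each dose. The sections agree with one another. Many steps in a fully remote trial rest on self-report, and most could be tightened. This stands to the extent that the point is an improvement to a working control and not the repair of a contradiction.

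The hazard is also described in mixed terms. Section 14 says the listed risks were observed with intravenous, not intranasal, administration, and Section 9.2 names hypersensitivity as the only contraindication, whereas Section 14 includes pregnancy and lactation. This stands, and it keeps the point minor. It does not remove it, because the sponsor chose to exclude pregnancy, to test weekly and to rely on those tests in Section 18.

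The detail may also sit elsewhere. The treatment delivery text in Section 9 points to a separate human-subjects document on safeguards, and Section 27 to a monitoring plan still to be developed. If either already has staff view the test, a cross-reference would settle the matter.

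Finally, a shown device could be an old one. That is true: a Veteran set on misreporting could still do so. The gain is limited to honest misreadings and to those who would skip a test but not present an old device.

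A reader might infer more than this, and the documents do not support it:

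- *That there is no pregnancy safeguard during treatment.* There is one; it is only unverified.
- *That staff will not look at the test.* The text is silent on this.
- *That setting 40 IU against the 60 IU in Section 9.2 measures the risk.* The 60 IU is a level with no recorded serious side effects of intranasal use; it is not a pregnancy threshold, and the section does not say whether that experience includes pregnancy.

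**Conclusion.** The point holds as a minor safety improvement. As written, a misread test, or a skipped test reported as negative, would not be caught before the dose it releases, although staff already have a video view of that dosing. Each wrong report releases one 40 IU dose, and one made at dose 8 is followed by no further scheduled test.

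The probability is low and cannot be quantified from the documents. It depends on how many of the 20 Veterans could become pregnant, possibly none, and on how often a test would be misread or skipped. The conclusion also assumes that no document outside those reviewed already requires staff to view the test. A reader might infer that participants face likely harm; the Protocol's own account of intranasal use does not support that. Confidence is medium.

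The SAP is written in the past tense, so dosing may be over. The design overview says the pilot will inform a proposal for a randomised trial, and the wording is worth changing before it is reused there.

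**What to change.** In the data collection part of Section 9, replace the spoken confirmation with: *before self-administration, the Veteran shows study staff that day's test device, marked with the date, on the VVC dosing call, with the partner out of the room; staff record the date and result in the coded study data.*

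Apply this to the 8 pre-dose tests only. The baseline test can stay as written, because the checked test before dose 1 precedes all dosing; this also avoids an extra video contact when the baseline assessment is done by phone. Do not put the result in the visit progress note, since that would place it in the medical record for little gain. Sections 10 and 15 say only that tests are performed and can stay as they are.

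The cost is one changed sentence, a short step on a call that already takes place, one dated entry per dose, and a line in the consent discussion. No staff, visits or tests are added. The downside is a minor privacy burden, reduced by having the partner leave the room. The check makes misread or skipped tests less likely to pass unnoticed, but it does not prove who took the test or when.
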